1. STUDY OBJECTIVES

1.1 Primary Objective

The primary endpoints are a clinically significant improvement in tolerance to inhaled methacholine (PD20) or a clinically significant decrease in exhaled nitric oxide. A clinically significant increase in tolerance to inhaled methacholine is defined as a 0.7 increase in the doubling dose for inhaled methacholine from the subjects baseline. A clinically significant decrease in exhaled nitric oxide is defined as a 20% decrease in subjects starting at a baseline of >50 ppb or a decrease of 10 ppb for subjects starting at a baseline of <50 ppb.

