6.2.3 Blinding

Ginger extract and placebo capsules have been pre-packaged and labeled with a code by the distributor (Atrium Innovations, Pure Encapsulations) and delivered to the research pharmacy at the Columbia University Medical Center. We do not anticipate any collected data offering evidence of a participant's assignment to a particular arm. All study data is collected objectively without an opportunity for the collected data to identify the study arm. For example, changes in methacholine PD20 and exhaled nitric oxide (primary outcomes) will vary over the course of the study in both ginger and placebo treated subjects. These variations will not be able to offer evidence of group membership and will only be informative after analysis in the aggregate.

The study PIs, [name], [name] are authorized to break the blind if there is a concern for subject safety, a serious adverse event or safety concerns raised by the DSMB. The PIs will contact the independent statistician who will be holding the codes. The PIs, Research Coordinator, study statistician(s), subjects and research pharmacy will be blinded. The research pharmacy will be notified as to randomization to drug A or B but will be unaware of which is ginger versus placebo.

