9.2 Sample Size and Randomization

We utilized published literature to identify the magnitude of change in our primary outcomes that are clinically relevant. As illustrated in the table in section 3, we calculated a need of 14 subjects per arm for the methacholine measurement and 16 subjects per arm for the exhaled nitric oxide assessment (same subjects studied in methacholine and exhaled nitric oxide assays). Thus we need 16 subjects per arm and anticipate a 10% attrition rate overall requiring 36 subjects. As illustrated in the table in section 3, an enhanced tolerance to inhaled methacholine of 0.7X the doubling dose is considered clinically significant.¹² We anticipate a S.D. of 0.6 in both groups and aim to achieve 80% power at the 0.05 significance level. This requires 14 subjects for each of the two arms. For exhaled nitric oxide with baselines starting at >50ppb, a 20% decrease is considered clinically significant. We expect a S.D. of ~ 37 and aim to achieve 80% power at the 0.05 level and will thus require 16 subjects for each of two arms.

Treatment Assignment Procedures

Subjects will be randomized to treatment A or B in a blinded fashion using the randomization algorithm within REDCap. The randomization module in REDCap implements a defined randomization model within the project, allowing the site to randomize the subjects. In this module, randomization model is defined as Drug A and Drug B in a 1:1 ratio. Drug A and Drug B may refer to placebo or active drug, however they are left coded as such to ensure blinding. The module creates a template allocation table, which the user uses to structure the randomization table to be imported. The module also monitors the overall allocation progress and assignment of randomized subjects to ensure balanced proportions of active drug and placebo. Only one site member will be allowed randomization privileges, but the site will confirm, and lock the specific data field to ensure that no data is altered after randomization. There is no stratification, and there are no variable block sizes.

Trial randomization codes for each individual subject will be retained within the REDCap data set as treatment A or B. The independent statistician retains the identity of A or B and does not disclose this to the study conductors. The planned breaking of the code will occur after data analysis is complete. Unplanned breaking of the code will occur if a medical condition mandates such an action.

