9.6 Data Analyses

We will compare the change in log-transformed methacholine reactivity (PD₂₀) in the ginger versus the placebo group using two-sample t-test. We will compare patients' initial PD₂₀ (day 0) to their subsequent PD₂₀ at days 28, 56 using paired t-test. It is possible that the PD₂₀ measurements on days 0, 28 and 56 could be influenced by the consumption of oral ginger 1 hour prior so we will also compare the PD₂₀ at

day 0 to those at 28 and 56. An acute benefit in methacholine tolerance will be reflected in a significant improvement between PD₂₀'s at days 0, 28 and 56 while a chronic improvement will be reflected in improved PD₂₀'s at days 28 and 56 compared to day 0.

Patients with asthma have remarkably consistent fractional exhaled nitric oxide (FeNO) levels when measured over time with mild-moderate asthmatics having FeNO values of approximately 40 ± 10 ppb.²² We will consider a 25% change in FeNO as biologically significant²³ comparing each patient's initial FeNO to their subsequent FeNO at days 28, 56 using paired t-test.

Data from prior studies does not support the existence of significant differences in the intervention effect between subgroups and thus subgroup analysis will not be performed.

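### FeNO, a primary outcome sized as ginger versus placebo, is given only within-patient paired tests, and no primary visit is named

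*Combined protocol and SAP*

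**What the plan says.** Section 1.1 sets the primary objective: "The primary endpoints are a clinically significant improvement in tolerance to inhaled methacholine (PD20) or a clinically significant decrease in exhaled nitric oxide". Section 9.5.1 repeats both outcomes, joined by the same conjunction, and lists Visits 4 and 5 (Days 28 and 56) without ranking them.

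Section 9.2 sizes each outcome as a comparison of two arms. For FeNO the plan will "aim to achieve 80% power at the 0.05 level and will thus require 16 subjects for each of two arms". For PD20: "We anticipate a S.D. of 0.6 in both groups and aim to achieve 80% power at the 0.05 significance level", which it says takes 14 per arm. FeNO therefore sets the requirement of 16 per arm, or 36 patients with 10% attrition. The table in section 3 labels the two groups as ginger and placebo and places PD20 and FeNO under Specific Aims 1 and 2.

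Section 9.6 then gives the tests. The change in log PD20 is compared "in the ginger versus the placebo group using two-sample t-test", followed by paired tests against baseline. For FeNO the only test is the comparison of each patient's "initial FeNO to their subsequent FeNO at days 28, 56 using paired t-test".

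Section 9.3 makes the primary analysis intention-to-treat in all randomized patients, but names no test.

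**The concern.** The placebo arm has no stated role in the test of the outcome that determined the trial's size. A before-after change within patients mixes any ginger effect with whatever else moves FeNO over 56 days, such as regression to the mean, better use of background inhalers, or season. Concurrent placebo patients are there to remove those influences, and a paired test leaves them out. A significant paired result for FeNO could then be reported as meeting a primary endpoint when placebo changed just as much.

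The unnamed visit adds a smaller problem. The written PD20 two-sample test could be run at Day 28, at Day 56 or at both, and a reader could not tell which result had been planned as decisive.

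**Working it through.** **1. Reproduce the plan's sample size.** Inputs from the table in section 3: FeNO 74 ± 37 versus 37 ± 34 ppb; PD20 1.07 ± 0.6 versus 1.73 ± 0.6 doubling doses. Section 9.2 gives 80% power and 0.05; two-sided is assumed because sidedness is not stated. Two-sample t-test: noncentrality = (difference/SD) × √(n/2), with 2n − 2 degrees of freedom.

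- FeNO: pooled SD = √((37² + 34²)/2) = 35.5; difference = 74 − 37 = 37. Power is 79% at 15 per arm and 81% at 16, so 16 per arm.
- PD20: difference = 1.73 − 1.07 = 0.66; SD 0.6. Power is 80% at 14 per arm.
- Attrition: 32/0.9 = 35.6, so 36.

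The plan's figures reproduce as two-arm comparisons. The FeNO sample size therefore assumes a test that section 9.6 does not write.

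**2. What the paired test does when ginger has no effect.** Suppose FeNO falls by the same mean amount in both arms. In a ginger arm of 16 at one visit, noncentrality = fall/(SD of change/√16) = 4 × fall/SD, with 15 degrees of freedom and a two-sided 0.05 critical value of 2.131. The falls are assumed. The SDs of change are also assumed: 37 and 10 are borrowed from the spreads of FeNO values in sections 9.2 and 9.6, which are not labelled as SDs of change, and 20 lies between them.

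| Common fall | SD 37 | SD 20 | SD 10 |
|---|---|---|---|
| 2 ppb | 4% | 6% | 11% |
| 5 ppb | 7% | 15% | 46% |
| 10 ppb | 17% | 46% | 96% |

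Entries are the chance of a significant fall in the ginger arm. A between-group t-test of the same data favours ginger in 2.5% of trials whatever the common fall, because the fall cancels.

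**3. The unranked visits.** Simulated null trials, 16 per arm, with the written PD20 two-sample test run at 0.05 at both visits: at least one significant result in 9.1%, 8.3% and 7.1% of trials for an assumed between-visit correlation of 0.5, 0.7 and 0.9. At one visit it is 5%.

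**4. Power of the proposed FeNO test.** It uses change from baseline, so the SD of change governs. With SDs of 37 and 34 and correlation r, SD of change = √(37² + 34² − 2r × 37 × 34), which is 35.6, 27.6 and 16.1 at r = 0.5, 0.7 and 0.9. For a 37 ppb difference at 16 per arm:

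| SD of change | Power at 0.05 | Power at 0.025 |
|---|---|---|
| about 35.5 | 81% | 72% |
| 27.6 | 96% | 92% |
| 16.1 | >99% | >99% |

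For PD20 (0.66, SD 0.6) at 16 per arm, power is 85% at 0.05 and 77% at 0.025.

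**The case against.** The strongest reply is that the FeNO sentence is incomplete rather than deliberate. The trial is randomized, section 9.3 calls for intention-to-treat, and section 9.2 sizes FeNO by arm, so a between-group test may be implied. That is plausible as to intent. But section 9.6 writes the between-group test for PD20 beside its paired test and does not do so for FeNO, and it does not say whether the FeNO paired test is run by arm or pooled. The omission stands as text to correct.

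A second reply is that shared change may be small. Section 9.6 describes FeNO in asthma as very stable over time, and no section reports a fall on placebo. This stands, and it is why the rates above are illustrations. A reader might take section 6.2.3, where the primary outcomes "will vary over the course of the study in both ginger and placebo treated subjects", as a forecast of a placebo fall. It is a blinding rationale: individual values fluctuate in both arms and so do not reveal allocation. It predicts no mean change.

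A third reply is that this is a 36-patient pilot with two Specific Aims, so adjusting for multiple outcomes is not obligatory. That also stands. If the aims are separate claims, no alpha split follows.

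A reader might also see a contradiction between section 9.2, where for baselines above 50 ppb "a 20% decrease is considered clinically significant", and section 9.6: "We will consider a 25% change in FeNO as biologically significant". The two use different terms and different references, so they need not conflict. Neither is tied to a trial-level test.

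**Conclusion.** The point holds for the FeNO test and the unnamed visit. As written, the only FeNO test can credit ginger with a change that placebo shares, and it is not the test for which 16 per arm was calculated. That conclusion rests on the text alone. The sizes (4–11%, 7–46% and 17–96% for common falls of 2, 5 and 10 ppb) rest on assumed falls and SDs of change. The 7–9% for PD20 at two visits rests on an assumed between-visit correlation of 0.5 to 0.9 and applies only if both visits are tested and either counts.

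A reader might infer that the plan carries a false-positive rate of 9–10% at one visit, or 13–18% over two, from having two primary outcomes. The documents do not support that: those rates need a between-group FeNO test at 0.05, which the plan does not write, and a single claim met by either outcome, which is only one of two possible readings.

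It is worth correcting before analysis. The documents give no go/no-go rule, so any effect on later decisions is inference. The choice of visit for the PD20 baseline, and the gap between the 20% decrease in section 9.2 and the 37 ppb difference in the section 3 table, are separate matters.

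**What to change.** - **Section 9.6.** Make the ginger-versus-placebo comparison of change in FeNO from baseline to Day 56 the primary FeNO test, reported with an estimate and 95% interval, in parallel with PD20. Label the paired tests descriptive.
- **Section 9.5.1.** Name Day 56 as primary and Day 28 as supportive for both outcomes. Section 9.5 already times the analysis to completion of Day 56, but that does not make it the primary visit.
- **Conditional.** State whether success on either PD20 or FeNO is one claim. If so, use Hochberg's procedure or 0.025 for each outcome at Day 56. If Specific Aims 1 and 2 are separate claims, say so; no split is then needed.

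**Cost.** The change is to wording, with no more patients. Naming Day 56 gives up a success seen only at Day 28. With separate claims no alpha is divided. Splitting to 0.025 at 16 per arm lowers PD20 power from about 85% to 77% (difference 0.66, SD 0.6). It lowers FeNO power for a 37 ppb difference from about 81% to 72% if the SD of change is near 35.5, or from 96% to 92% if it is near 27.6. The documents do not give the SD of change, so the plan should state the value it assumes.

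### Section 9.6 analyses PD20 on the log scale but names no scale for FeNO; pre-specifying log FeNO would gain about 0 to 25 points of power, depending on spread and correlation

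*Combined protocol and SAP*

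**What the plan says.** Section 9.6 (Data Analyses) treats the two primary outcomes differently. For airway responsiveness it says "We will compare the change in log-transformed methacholine reactivity (PD₂₀) in the ginger versus the placebo group using two-sample t-test". For FeNO it names a within-patient comparison of "initial FeNO to their subsequent FeNO at days 28, 56 using paired t-test". It names no transformation for FeNO, and no other section supplies one.

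The FeNO effect is stated in more than one way:
- Section 9.6: "We will consider a 25% change in FeNO as biologically significant".
- Section 1.1 (Primary Objective) and the Section 3 table: a "20% decrease in subjects starting at a baseline of >50 ppb or a decrease of 10 ppb for subjects" starting below that level. The criterion is therefore relative above 50 ppb and absolute below it.

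The spread of FeNO also appears in more than one form:
- The Section 3 sample size table gives 74 ± 37 and 37 ± 34 ppb.
- Section 9.2 says "We expect a S.D. of ~ 37 and aim to achieve 80% power at the 0.05 level".
- Section 9.6 cites "FeNO values of approximately 40 ± 10 ppb" for mild-to-moderate asthma.

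Sections 4.1 and 4.2 set no FeNO limit for entry.

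**The concern.** A t-test on ppb change estimates a mean difference in ppb. If ginger lowers FeNO by a roughly constant proportion, patients who start high contribute large absolute changes and patients who start low contribute small ones. The test then carries extra variance that comes only from the spread of starting levels, and its estimate is not a percent change. A difference in log FeNO back-transforms directly to a percent reduction, which is how Section 9.6 proposes to judge the effect. The plan already accepts this reasoning for PD20.

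At stake are the precision and interpretability of a primary outcome in a trial with 16 evaluable patients per arm. If raw ppb was not intended, the scale of a primary analysis is open, and that too should be settled before the data are analysed.

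**Working it through.** **1. The plan's own figure.** The Section 3 means give a difference of 74 − 37 = 37 ppb, and Section 9.2 gives SD 37. With two-sided 0.05 (sidedness is not stated) and 80% power, n per arm = 2 × (1.960 + 0.842)² × 37² / 37² = 15.7, so 16. Adding 10% attrition to 32 gives 36. The stated 16 per arm is therefore reproduced by an untransformed ppb calculation. It rests on a halving of FeNO, so the power figures below, for a 25% fall, should not be expected to match 80%.

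**2. Shape implied by the three figures.** Log SD = √ln(1 + CV²), where CV = SD/mean. The last column is the share of a normal model that falls below zero, which is impossible for FeNO.

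| FeNO (ppb) | Source | CV | Log SD | Normal mass below 0 |
|---|---|---|---|---|
| 37 ± 34 | Section 3 | 0.92 | 0.78 | 13.8% |
| 74 ± 37 | Section 3 | 0.50 | 0.47 | 2.3% |
| 40 ± 10 | Section 9.6 | 0.25 | 0.25 | 0.003% |

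A normal model is untenable at 37 ± 34, doubtful at 74 ± 37 and acceptable at 40 ± 10.

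**3. Power, raw against log.** Simulation with 40,000 runs per cell, log-normal FeNO, 16 per arm, two-sided 0.05, a 25% fall with ginger and none with placebo. The documents give no baseline–follow-up correlation (r), so 0.5 to 0.9 is assumed; r applies to log FeNO. Entries are power in percent, raw then log. Gains were taken before rounding.

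| FeNO | r | Paired, ginger arm | Gain | Two-sample on change | Gain |
|---|---|---|---|---|---|
| 37 ± 34 | 0.5 | 20.1 → 27.9 | 7.8 | 11.7 → 17.0 | 5.4 |
| | 0.7 | 30.0 → 42.9 | 12.9 | 16.2 → 25.5 | 9.3 |
| | 0.8 | 40.4 → 58.3 | 17.9 | 21.3 → 35.2 | 13.9 |
| | 0.9 | 66.7 → 86.3 | 19.6 | 36.6 → 61.1 | 24.4 |
| 74 ± 37 | 0.5 | 56.1 → 62.5 | 6.4 | 29.9 → 38.7 | 8.8 |
| | 0.7 | 76.9 → 83.6 | 6.7 | 44.4 → 57.8 | 13.4 |
| | 0.8 | 90.2 → 94.9 | 4.7 | 59.3 → 75.0 | 15.7 |
| | 0.9 | 99.4 → 99.9 | 0.5 | 85.2 → 96.1 | 11.0 |
| 40 ± 10 | 0.5 | 98.9 → 99.2 | 0.3 | 81.9 → 88.9 | 7.1 |
| | 0.7 | 100 → 100 | 0.0 | 95.8 → 98.5 | 2.8 |
| | 0.8 | 100 → 100 | 0.0 | 99.3 → 99.9 | 0.6 |
| | 0.9 | 100 → 100 | 0.0 | 100 → 100 | 0.0 |

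The log scale is equal or better in every cell. With no effect, rejection stays at about 4 to 5% on both scales. For a 20% fall the two-sample gain is 0.2 to 16.5 points.

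**4. Adding the baseline covariate.** Log FeNO with baseline log FeNO as covariate gives 21%, 38% and 62% at 37 ± 34 (r = 0.5, 0.8, 0.9), and 47%, 78% and 97% at 74 ± 37. Covariate adjustment alone does not close the gap at 37 ± 34: on raw ppb it reaches 27% at r = 0.8 and 45% at r = 0.9.

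**5. If the log is the wrong scale.** With additive, normal data at 40 ± 10, the largest loss found was 3.6 points: the paired test, a 4 ppb fall and r = 0.8, from 65.8% to 62.2%.

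**The case against.** Much of the case for leaving the text alone concerns how far the point can be pushed, and most of that stands.

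- **A raw-ppb test is an inference.** A reader might infer that the plan chose raw ppb. It does not say so. The inference rests on the missing transformation and the ppb-based sample size. Because Section 9.6 speaks of a 25% change from each patient's initial value, per-patient percent change is another possible reading. A two-sample test on percent change gives 32% and 59% power at 37 ± 34 (r = 0.8, 0.9) against 36% and 61% for the log, and 74% and 96% at 74 ± 37 against 76% and 96%. On that reading the log gains only about 0 to 4 points in these cells.
- **The spread is not settled.** A reader might infer that FeNO varies about as much as its mean, and that the log therefore recovers 14 to 24 points. That fits only 37 ± 34, with an assumed correlation of 0.8 to 0.9 and a two-sample test. At 40 ± 10 the gain is 0 to 7 points. However, Section 9.6 attaches 40 ± 10 to mild-to-moderate asthma, while the trial enrols mild to severe asthma with no FeNO limit, and Section 9.2 plans with an SD of about 37.
- **The correlation is not given.** Section 9.6 speaks of "remarkably consistent fractional exhaled nitric oxide (FeNO) levels when measured over time", which favours the higher values but supplies no number.
- **The effect is not purely relative.** Below 50 ppb the primary criterion is an absolute 10 ppb. At 40 ± 10 a normal model puts Φ((50 − 40)/10) = 84% of patients under that rule, so a ratio of geometric means does not map fully onto Section 1.1.
- **The simulation favours the log.** A log-normal model with a proportional effect is the log's own model, and step 5 of the working shows a small loss under the opposite one.

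None of this argues for leaving the scale unstated.

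**Conclusion.** The point holds in a limited form. FeNO is a primary outcome with no stated analysis scale, next to another primary outcome that is log-transformed. Its effect is framed mostly in percent, and the planning figures make a normal model on ppb doubtful. For a 25% fall with 16 per arm and log-normal data, the log scale gains about 0 to 25 points for a between-arm test on change (about 5 to 25 at 37 ± 34, 9 to 16 at 74 ± 37, 0 to 7 at 40 ± 10) and about 0 to 20 for the paired test as written. These ranges rest on the assumed correlation of 0.5 to 0.9 and on which of the three spreads applies.

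The documents do not support any single figure within the ranges, nor a claim that the change is free. The estimand changes, and up to about 4 points could be lost if changes are additive and normal. Nor would the log scale alone give a randomised comparison, because Section 9.6 names no ginger-versus-placebo test for FeNO. That is a separate and larger gap, which the wording below also fills.

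**What to change.** In Section 9.6, state that FeNO is analysed as log FeNO. Compare ginger with placebo using follow-up log FeNO as the response and baseline log FeNO as covariate, and back-transform the difference to a percent reduction with its 95% CI. Keep the Section 1.1 definition (20% above 50 ppb, 10 ppb below) as a separate descriptive responder summary by arm, so the mixed-scale criterion is still reported.

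The cost is a sentence or two in the analysis section, with no new data, visits or patients. The main result would be read as a ratio of geometric means rather than a ppb difference, with the small possible power loss given above.

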10. DATA COLLECTION AND QUALITY ASSURANCE

10.1 Data Collection Forms

Information for each participant will be collected by the lead study clinical coordinator ([name]) and the PIs ([name] and [name]) and recorded on case report forms (please see attachments under appendices, section 15 of this document) that will be electronically recorded within REDCap. All 3 of these individuals will be blinded as to the study group of the subject.

10.2 Data Management

Access to clinical data will be limited to the clinical study coordinator, [name] and [name]. All data will be stored within REDCap via desktop computers that are encrypted, password protected and physically located on the Columbia University campus. All participants will be assigned a unique non-identifying number for which all their data and blood samples will be labeled. The key for this list will only be retained by the 3 individuals and devices named above. No personal identifying information will be available outside of this coded list on these protected devices.

Data from this single site study will be stored within REDCap.

The case report forms for each study visit are attached in the appendices, section 15 of this document.

10.3 Quality Assurance

10.3.1 Training

All individuals involved in this study have completed all institutional and IRB-required training for participation in human clinical trials including but not limited to GCP and HIPPA training. The study coordinator has been trained in the administration of spirometry, methacholine provocation testing, administration of bronchodilators and phlebotomy. All of these procedures will occur in a monitored clinical setting (the John Edsall-John Wood Asthma Center at Columbia University Medical Center).

